6.1. Recruitment strategy

Participants may be recruited by use of an advertisement +/- registration form formally approved by the ethics committee. All participants will sign and date the informed consent form (ICF) before any study-related procedures can be performed. Doctors enrolling the patients are responsible for obtaining the ICF before enrolling patients (i.e. before making screening test)

The volunteer's GP (Medico di Medicina Generale) will be informed and relevant clinical information registered if it is possible.

6.2. Adults-Cohort

Healthy people aged 18–55 years and full details of the eligibility criteria are described in section 6.5.

6.3. Elderlies-Cohort

Healthy people aged 65–85 years and full details of the eligibility criteria are described below

6.4. Inclusion criteria

A subject must meet all of the following criteria to be eligible to participate in this study:

1. Provides written informed consent prior to initiation of any study procedures.
2. Be able to understand and agrees to comply with planned study procedures and be available for all study visits.
3. Agrees to the collection of venous blood per protocol.
4. Confirms to have not donated blood three months before the study
5. Agrees to refrain from blood during the study and until the three months after the end of the study.
6. Body Mass Index 18-29 kg/m², inclusive, at screening.
7. Premenopausal women must agree to use one acceptable primary form of contraception.
8. Premenopausal women must have a negative urine pregnancy test the day of vaccination and are routinely using - and willing to use up to six months from vaccine administration - an effective method of birth control resulting in a low failure rate (i.e., hormonal contraception, condoms in combination with a spermicidal cream, male partner sterilization-vasectomy or total sexual abstinence).
9. Oral temperature ≤37.0 degrees Celsius the day of the administration of the vaccine
10. Pulse no greater than 100 beats per minute.
11. Systolic blood pressure (BP) is 85 to 139 mmHg, inclusive the day of vaccination.
12. Should not show laboratory values outside the normal range which may have clinical significance even in absence of specific signs or symptoms.

6.5. Exclusion Criteria

A subject who meets any of the following criteria will be excluded from participation in this study:

1. Positive serology for anti-HIV-Ab
2. Positive HbBsAg
3. Positive anti-HCV-Ab
4. Positive for SARS-CoV-2 (either anti-S-Ab or anti-N-Ab)
5. Acute illness, as determined by the site PI or appropriate sub-investigator, the day of vaccination.
6. Breastfeeding women
7. Autoimmune and hyper-inflammatory condition
8. History of atopy (or any IgE associated condition) who had required treatment over the last 6 months;
9. History of hypersensitivity or severe allergic reaction (e.g., anaphylaxis, generalized urticaria, angioedema, other significant reaction) to any previous licensed or unlicensed vaccines;

10. Assumption of any immunomodulatory medication over the last 4 months (including, but not limited to, systemic corticosteroids, allergy injections, immunoglobulin, interferon, immunomodulators, cytotoxic drugs, or other similar or toxic drugs). The use of low dose topical, ophthalmic, inhaled, and intranasal steroid preparations will be permitted.
11. Presence of self-reported or medically documented significant medical condition
12. Presence of self-reported or medically documented significant psychiatric condition
13. Significant cardiovascular disease needing therapy or history of myocarditis or pericarditis or heart surgery. Patients in treatment with Sartans or ACE-Inhibitors and good response to therapy may be included.
14. Neurological or neurodevelopmental conditions (e.g., history of migraines in the past 5 years, epilepsy, stroke, seizures in the last 3 years, encephalopathy, focal neurologic deficits, Guillain-Barré syndrome, encephalomyelitis or transverse myelitis).
15. Ongoing malignancy or recent diagnosis of malignancy in the last five years excluding basal cell and squamous cell carcinoma of the skin, which are allowed.
16. Primary or secondary immunodeficiency of any cause.
17. Participated in another investigational study involving vaccination of biologic compounds in the last 12 months.
18. Currently enrolled in or plans to participate in another clinical trial with an investigational agent that will be received during the study-reporting period.
19. Administration of immunoglobulins and/or any blood or blood products within the 4 months before the first vaccine administration or at any time during the study.
20. Has any significant disorder of coagulation.
21. Has any chronic liver disease, including fatty liver.
22. Has a history of alcohol abuse or other recreational drug use within 6 months before the first vaccine administration.
23. Has any abnormality or permanent body art (e.g., tattoo) that would interfere with the ability to observe local reactions at the injection site (deltoid region).
24. Received or plans to receive additional vaccination within 4 weeks before or after each vaccination.
25. Has been reported as a case (confirmed or probable) of COVID-19 from the regional health system
26. Has any clinical conditions that, in the opinion of the site PI or appropriate sub-investigator, precludes study participation, this includes any acute, subacute, intermittent or chronic medical disease or condition that would place the subject at an unacceptable risk of injury, render the subject unable to meet the requirements of the protocol, or may interfere with the evaluation of responses or the subject's successful completion of this trial

6.6. Lost to follow-up and withdrawal

In accordance with the principles of the current revision of the Declaration of Helsinki and any other applicable regulations, a participant has the right to withdraw from the study at any time and for any reason, and is not obliged to give his or her reasons for doing so. The Investigator may withdraw a participant at any time in the interests of the participant's health and well-being. The reason for withdrawal will be recorded in the CRF (if available). If withdrawal is due to an AE, appropriate follow-up visits or medical care will be arranged, with the agreement of the participant, until the AE has resolved.

Investigator may decide to replace a participant withdrawn or lost to follow-up if that is possible within the specified enrollment timeframe.

If a participant withdraws from the study, blood samples collected before their withdrawal from the trial will be used/stored unless the participant specifically requests otherwise. In all cases of participant withdrawal, except those of complete consent withdrawal, long-term safety data collection, including some procedures such as safety bloods, will continue as appropriate if subjects have received vaccine.

6.7. *Compliance with Dosing Regime*

All doses in this vaccine study will be administered under the supervision of a medical investigators by registered healthcare workers and recorded in the CRF. The study medication will be at no time in the possession of the participant and compliance will, therefore, not be an issue.

6.8. *Pregnancy*

Should a participant become pregnant during the trial, she will be followed up as other volunteers and in addition will be followed until pregnancy outcome. We will not routinely perform venopuncture in a pregnant volunteer.

7. Clinical procedures

All participants will receive the GRAd-COV2 vaccine and undergo follow-up at specific endpoint for a total of 24 weeks. All follow-up visit will include a medical visit and a blood sampling. Moreover, all participants will receive a telephone number to be contacted for receiving assistance should any medical condition occur, potentially associated with the vaccination. Additional visits or procedures may be performed at the discretion of the investigators based on participants needs.

7.1. *Vaccination procedure*

Vaccines will be administered intramuscularly in the deltoid of non-dominant arm according to different doses:

- A. Dose 5×10^{10} vp (arm 1 and arm 4)
- B. Dose 1×10^{11} vp (arm 2 and arm 5)
- C. Dose 2×10^{11} vp (arm 3 and arm 6)

The injection site will be covered with a sterile dressing and the participants will stay in observation per 4 hours, in case of immediate adverse events. Investigator will decide whether the participant can leave or need additional time in hospital monitoring.

All participants will be vaccinated with the same procedure and according to the same schedule of clinical record. A standard electronic case report forms (e-CRF) will be produced and filled in.

7.2. *Medical visit*

Medical visit will be carried out at the endpoints indicated in the schedule of procedures and will always include a check of medical history, physical examination, weight and height (at screening only), pulse, blood pressure, after 10 min rest in sitting position, and body temperature.

7.3. *Blood test and other analysis for monitoring safety*

Biological testing for monitoring safety will be carried out at the endpoints indicated in the schedule of procedures at the laboratory of the clinical centers that enroll volunteers and will include:

- A. Full Blood Count
- B. Urine analysis
- C. Biochemistry: Sodium, Potassium, , , Albumin, Liver Function Tests (ALT, ALP, Bilirubin total and fractionated), Renal function (Creatinine and BUN), lactate dehydrogenases (LDH), alkaline phosphatases (ALP)
- D. Diagnostic serology: HBsAg, HCV antibodies, HIV antibodies (specific consent will be gained prior to testing blood for these blood-borne viruses)
- E. Coagulation: aPTT (ratio), PT (ratio) and INR.

Urine will be tested for pH, Glucose Protein, Haemoglobin, Leukocyte esterase, Ketones, Bilirubin, Urobilinogen and Nitrites at screening. For female participants only, urine will be tested for beta-human chorionic gonadotrophin (β -HCG) at screening.

Participants presenting with respiratory symptoms consistent with COVID-19 infection will undergo to molecular test for SARS-CoV-2 and admitted to hospital in isolation room until a negative is available.

Additional safety blood tests may be performed if clinically relevant at the discretion of the medically qualified investigators.

Item	Time of the visit since vaccination									Type of intervention
	Scr	T0	D2	W1	W2	W4	W8	W12	W24	
Window (days)	≤ 21	0	0	±1	±1	±2	±4	±7	±14	
Informed consent	x									Procedures
Eligibility	x									
Vaccination		x								
AE reporting		x	x	x	x	x	x	x	x	
Diary card		A				B				
Medical history	x									
Physical examination	x	x	x	x	x	x	x	x	x	Medical visit
TC	x	x	x	x	x	x	x	x	x	
SpO2 %	x	x	x	x	x	x	x	x	x	
Pulse	x	x	x	x	x	x	x	x	x	
Blood pressure	x	x	x	x	x	x	x	x	x	
Urine analysis	x									
Urine B-HCG	x	x								Urine
Blood counts	x	x	x	x	x	x	x	x	x	
Biochemistry	x	x	x	x	x	x	x	x	x	
Coagulation	x									
HIV-Ab	x									
HBsAg and HCV	x									
HLA Typing				x						Blood test
SARS-CoV-2 Serology *	x									
CLIA anti-S (IgG)		x		x	x	x	x	x	x	
CLIA anti-N (IgG)		x		x	x	x	x	x	x	
Micro neutralization					x				x	
Elispot SARS-CoV-2		x			x	x	x	x	x	
Total blood volume (mL)	36	60	10	27	60	60	60	60	60	433

Figure 9 Timing of participant follow-up after vaccination. Scr=screening to be done no more than 21 days before vaccination; T0=day of the vaccination; D2= day 2 after vaccination; W1= one week after vaccination; W2= two weeks after vaccination W4= four weeks after vaccination; W8= eight weeks after vaccination; W12= twelve weeks after vaccination; W24= twenty-four weeks after vaccination. A) Diary given to participants; B) Diary received from participants.

* This is any serological assay to detect anti-SARS-CoV-2 total IgG which is validated for clinical use in Italy (i.e. validated for diagnosis of SARS-CoV-2 infection)

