4.2.2. Secondary endpoints (immunogenicity)

The secondary endpoint for the study is the assessment of cellular and humoral immune response elicited by the vaccine at different time weeks after the administration of three different doses of vaccine, namely 5×10^{10} , 1×10^{11} and 2×10^{11} viral particles, either in adults and elderlies. This include:

- A. CLIA to quantify antibodies to SARS-CoV-2 S-protein (anti-S-Ab) at week 2, 4, 8, 12 and 24 in adults who receive either 5×10^{10} , 1×10^{11} and 2×10^{11} viral particles;
- B. CLIA to quantify antibodies to SARS-CoV-2 S-protein (anti-S-Ab) at week 2, 4, 8, 12 and 24 in elderlies who receive either 5×10^{10} , 1×10^{11} and 2×10^{11} viral particles;
- C. CLIA to quantify antibodies to SARS-CoV-2 N-protein(anti-N-Ab) at week 2, 4, 8, 12 and 24 in adults who receive either 5×10^{10} , 1×10^{11} and 2×10^{11} viral particles;
- D. CLIA to quantify antibodies to SARS-CoV-2 N-protein(anti-N-Ab) at week 2, 4, 8, 12 and 24 in elderlies who receive either 5×10^{10} , 1×10^{11} and 2×10^{11} viral particles;
- E. SARS-CoV-2 micro-neutralization assay to quantify neutralizing antibody activity to the virus at week 4 and 24 in adults who receive either 5×10^{10} , 1×10^{11} and 2×10^{11} viral particles;
- F. SARS-CoV-2 micro-neutralization assay to quantify neutralizing antibody activity to the virus at week 4 and 24 in elderlies who receive either 5×10^{10} , 1×10^{11} and 2×10^{11} viral particles;
- G. Ex vivo IFN γ ELISpot responses to SARS-CoV-2 S-protein at week 2, 4, 8, 12 and 24 in adults who receive either 5×10^{10} , 1×10^{11} and 2×10^{11} viral particles
- H. Ex vivo IFN γ ELISpot responses to SARS-CoV-2 S-protein at week 2, 4, 8, 12 and 24 in elderlies who receive either 5×10^{10} , 1×10^{11} and 2×10^{11} viral particles

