7.4. Immunogenicity analysis

Tests for assessing immunogenicity will be carried out at INMI Lazzaro Spallanzani laboratory at the endpoints indicated in the schedule of procedures. Management of samples and methodology of testing are reported in section 6. Testing for immunogenicity includes:

- A. CLIA to quantify antibodies to SARS-CoV-2 S-protein (anti-S-Ab)
- B. CLIA to quantify antibodies to SARS-CoV-2 N-protein(anti-N-Ab)
- C. SARS-CoV-2 micro-neutralization assay to quantify neutralizing antibody activity to the virus
- D. Ex vivo IFN-gamma ELISpot responses to SARS-CoV-2 S-protein

Other exploratory immunological assays including analysis polyfunctional T cell analysis and other antibody assays will be performed at the discretion of the investigators.

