10.2. Statistics analysis

This is a descriptive safety study, where participants will be vaccinated with different doses of GRAd-COV2 against SARS-CoV-2. Forty-five participants per age cohort (for a total of 90 subjects) will be vaccinated in total. This sample size should allow an estimation to be made of the frequency and magnitude of outcome measures, rather than aiming to obtain formal statistical significance for differences between groups.

Safety data will be presented according to frequency, severity and duration of adverse events. The primary analysis for immunogenicity will be to assess the difference in magnitude of SARS-CoV-2 specific T-cell and antibody responses between the groups. We will assess vaccine immunogenicity by comparing the change in these immunological parameters from baseline to different endpoints. At the end of the study, we expect to

6 measures per participant for T-cell response and antibody level. We will explore the possibility to describe kinetics of these parameters through non-parametric test for comparison of:

- A. *within-the-arm medians* at different times (i.e. baseline vs. either week-2, week-4, week-8, week-12 and week 24) between groups at different follow-up time);
- B. *within the Adults-Cohort medians* at specific time (i.e. Arm-1 vs. either Arm-2 or Arm-3 at baseline, week-2, week-4, week-8, week-12 or week-24).
- C. *within the Elderlies-Cohort medians* at specific time (i.e. Arm-4 vs. either Arm-5 or Arm-6 at baseline, week-2, week-4, week-8, week-12 or week-24).
- D. *Across the cohort medians at specific time* (i.e. Arm-1 vs. Arm-4; Arm-2 vs Arm-5; Arm-3 vs. Arm-6 at baseline, week-2, week-4, week-8, week-12 or week-24)

Explorative kinetics model based on regression techniques for correlated measures will be carried out if normal distribution of data is proven.

11. Data Management

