### 4.2 General Presentation Considerations

The overall outline of the scheduled assessment and other study procedures can be found in the Schedule of Assessment, [Table 5](#). In the following, the data handling conventions should be interpreted within the framework of the Schedule of Assessment.

The date of Enrolment Visit (Time 0) is defined as Day 1. All other study days will be labeled relative to Day 1.

- For observation/event dates on or after Day 1, study day for an observation/event date is derived as:  
Observation/event date – visit Time 0 date + 1 day, which could be Day 1, Day 2, Day 3, etc.
- For observation/event dates prior to Day 1, study day for an event date is derived as:  
Observation/event date – visit Time 0, which could be Day -1, Day -2, etc., referring to 1 day, 2 days, etc., prior to Day 1, respectively.
- Day 0 is not defined.

Baseline is considered as the result of last non-missing evaluation before vaccine administration, unless specified otherwise.

End of Study is defined as the last available post-treatment assessment.

Continuous data will be summarized in terms of the mean, standard deviation (SD), median, minimum, maximum and number of observations, unless otherwise stated.

Count data will be summarized in terms of the median, lower and upper quartile, minimum, maximum and number of observations, unless otherwise stated. Geometric mean titer will be provided also for result in titer.

Categorical data will be summarized in terms of the number of subjects providing data at the relevant time point (n), frequency counts and percentages. Any planned collapsing of categories will be detailed in the SAP text and the data displays.

The minimum and maximum will be reported to the same number of decimal places as the raw data recorded in the database. The mean, median, lower quartile and upper quartile will be reported to one more decimal place than the raw data recorded in the database. The SD will be reported to two more decimal places than the raw data recorded in the database. In general, the maximum number of decimal places reported shall be four for any summary statistic. Confidence intervals will be presented to one more decimal place than the raw data.

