#### 4.14 Interim Analyses

There will be two interim analyses (IAs) before general database lock and provision of final study results.

Each interim analyses will be preceded by a DRM focusing on the subjects to be included in the actual IA, i.e. for the first interim analysis (Deliverable 1) the target subject pool will be those who were enrolled for Arm 1 – 3 (Adults), for the second interim analysis (Deliverable 2) the target pool will be those who were enrolled for Arm 4 – 6 (Elderlies).

The first interim analysis will use data collected in Arm 1 – 3 up to the last subject in Arm-3 completed its Week 4 visit (Adults, highest dose). The second interim analysis will use data collected in Arm 4 – 6 up to last subject in Arm-6 completed its Week 4 visit (Elderlies, highest dose).

All outputs specified in the study's TLF Specification will be provided for both IAs. Grouping of IA summaries will follow guidelines specified in Section 4.2.1.

Selected immunogenicity endpoints such as ELISpot and nAb data will be analyzed at single timepoints during interim analyses. Results of ELISpot and nAb will be reported only for Week 2 and Week 4, respectively.

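### Protocol Figure 9 schedules the microneutralisation assay at W2 and W24, but the secondary endpoints, the SAP schedule and both interim analyses use W4 and W24

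*Protocol*

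**What the plan says.** Protocol 4.2.2 defines endpoint E as "SARS-CoV-2 micro-neutralization assay to quantify neutralizing antibody activity to the virus at week 4 and 24 in adults", and endpoint F as "neutralizing antibody activity to the virus at week 4 and 24 in elderlies", each covering the three dose arms of its cohort.

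The schedule of procedures (Protocol 7.3, Figure 9) marks the row "Micro neutralization" in the W2 and W24 columns only. On which text governs, Protocol 7.4 states: "Tests for assessing immunogenicity will be carried out at INMI Lazzaro Spallanzani laboratory at the endpoints indicated in the schedule of procedures".

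SAP Table 5 (Appendix 6.1) marks the assay at W4 and W24. For the two interim analyses, SAP 4.14 states: "Results of ELISpot and nAb will be reported only for Week 2 and Week 4, respectively".

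On baseline, Protocol 10.2 says of T-cell and antibody responses in general: "We will assess vaccine immunogenicity by comparing the change in these immunological parameters from baseline to different endpoints". It also expects "6 measures per participant for T-cell response and antibody level". SAP 4.2 defines the term: "Baseline is considered as the result of last non-missing evaluation before vaccine administration, unless specified otherwise". SAP 4.10 summarises the neutralisation titre by visit, with a geometric mean titre at each time point and results below 1:10 set to 5. Neither schedule has a T0 mark for this assay.

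**The concern.** The protocol contradicts itself on when a secondary endpoint is measured, and the side that disagrees with everything else is the one section 7.4 tells the laboratory to follow. A laboratory working only from Figure 9 would run the assay at W2, a time point that no endpoint or SAP analysis of this titre uses, and would not run it at W4, which they all use.

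The W4 titre feeds the two interim reports. Under Protocol 4.2.5 these include a preliminary immunogenicity analysis meant to help choose doses for a later phase 2/3 trial. Microneutralisation is the only listed secondary measure of functional antibody activity against the virus, so a missing or delayed W4 result would weaken that comparison.

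**Working it through.** **1. Time points side by side**

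| Source | T0 | W2 | W4 | W24 |
|---|---|---|---|---|
| Protocol Figure 9 | – | x | – | x |
| Protocol 4.2.2, E and F | – | – | x | x |
| SAP Table 5 | – | – | x | x |
| SAP 4.14 (interim only) | – | – | x | not applicable |

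Only W24 is common to Figure 9, the endpoints and SAP Table 5.

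**2. Is the Figure 9 mark a displaced cell?** The header has nine visit columns: Scr, T0, D2, W1, W2, W4, W8, W12, W24. The microneutralisation row has the same number of cells as its neighbours, with marks in visit columns 5 (W2) and 9 (W24). The ELISpot row directly below maps to T0, W2, W4, W8, W12 and W24. That is six time points, matching the six measures in Protocol 10.2. The blood-volume row also reproduces its stated total:

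36 + 60 + 10 + 27 + 60 + 60 + 60 + 60 + 60 = 433 mL.

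The table therefore appears intact. A shifted cell is unlikely but cannot be excluded without looking at the printed figure.

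**3. Could a W2 sample count as W4?** The Figure 9 windows are ±1 day at W2 and ±2 days at W4.
- W2: 14 ± 1 = days 13 to 15 after vaccination.
- W4: 28 ± 2 = days 26 to 30 after vaccination.

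They do not overlap.

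**4. Size if Figure 9 is followed literally**
- Planned endpoint measurements: 90 participants × 2 visits = 180.
- Covered by Figure 9 (W24 only): 90 × 1 = 90.
- Unscheduled: 180 − 90 = 90, all at W4.
- Per interim analysis: 0 of 45 W4 results scheduled in adults, and 0 of 45 in elderlies.
- With the mark moved to W4: 180 of 180 scheduled.

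**5. Baseline.** Scheduled tests per participant are 2 for microneutralisation, 6 for ELISpot and 7 for each CLIA (6 without W1). The six-measure plan in Protocol 10.2 fits ELISpot, and CLIA apart from W1; it cannot describe an assay run at two visits. Pre-vaccination microneutralisation tests number 0 in both schedules. The only neutralising-antibody test stated at enrolment is the one against the GRAd32 vector (Protocol 4.2.3), which is a different assay. Adding T0 would give 90 × 3 = 270 measurements.

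**The case against.** **The laboratory may never have relied on Figure 9.** The endpoint definitions, the SAP schedule and the interim plan all say W4. The SAP is based on Protocol Version 2.0, and it cites the safety blood tests at protocol section 8.3, whereas they are at 7.3 in the protocol supplied. SAP Table 5 also differs from Figure 9 elsewhere, for example in the screening window (28 against 21 days) and an added ECG row. The mark may already have been corrected in the version in force. This limits confidence about what was done, but the contradiction between 4.2.2 and Figure 9 lies inside the supplied protocol and stands.

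**A missed W4 assay is probably recoverable.** Figure 9 draws 60 mL at W4 whatever happens to this row, Protocol 4.2.3 needs W4 serum for the vector assay, and Protocol 15.6 says samples are stored indefinitely. This stands. A reader might infer that all 90 participants would have no W4 value and that both interim tables would be empty. The documents show only that those results would be unscheduled.

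**The missing T0 test is a weaker point than it looks.** A reader might infer that a planned change from baseline or seroconversion analysis is made impossible. The documents do not support that. Endpoints E and F are defined as activity at two visits, not as change. Protocol 10.2 does not name this assay when it speaks of baseline. The SAP plans no fold rise or seroconversion for the titre. Nor does the age of the screening serology make baseline status unknown: anti-S and anti-N CLIA are both scheduled at T0, and seropositive volunteers are excluded (Protocol 6.5, criterion 4). What remains is narrower. Binding IgG is not a neutralisation result, neither document states that baseline is taken as below 1:10, and SAP 4.15 does not record that the general change-from-baseline plan is not applied to this titre.

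**Conclusion.** The point holds as an internal inconsistency in the assay schedule. Figure 9 says W2 and W24; every other statement of this endpoint's timing that covers the interim period says W4. Read literally, with section 7.4 giving the schedule precedence, 90 of 180 planned measurements are unscheduled, 45 of them in each interim report. W24 is unaffected.

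This rests on three assumptions: that the printed figure carries the mark under W2, that the supplied protocol is the version sites used, and that the laboratory worked from the schedule rather than the endpoint text. None can be settled from the documents, so the figure of 90 is the exposure under a literal reading, not an expected loss.

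Microneutralisation is one of several unranked secondary measures; the documents do not call it key. The absent T0 test is a secondary matter of completeness in a descriptive study with no planned hypothesis tests.

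**What to change.** 1. Check Figure 9 in the protocol version in force. If the mark is still at W2, move it to W4 so that it agrees with Protocol 4.2.2, SAP Table 5 and SAP 4.14. This changes one cell and needs no extra blood.
2. Confirm with the laboratory which visits were assayed. If W2 was run instead of W4, assay stored W4 serum where enough remains, and identify any W2 results as additional to the planned analysis.
3. Optional: settle the baseline question in either of two ways.
   - Run the assay on T0 serum already drawn and add T0 to both schedules. The cost is up to 90 extra runs, each a duplicate titration under BSL3 conditions (Protocol 14.1), and it depends on enough serum remaining.
   - Add a sentence to SAP 4.10 saying that this titre is summarised by visit only, with no change from baseline. This costs nothing beyond the edit.
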